14.2 Data Capture Methods and Management

Data for this trial will be collected using City of Hope's electronic capture system that is compliant with 21 CFR Part 11.

Study personnel will enter data from source documents corresponding to a subject's visit into the protocol-specific electronic Case Report Form (eCRF).

14.3 Case Report Forms/Data Submission Schedule

Study personnel will enter data from source documents corresponding to a subject's visit into the protocol-specific electronic Case Report Form (eCRF) when the information corresponding to that visit is available.

The investigator is responsible for all information collected on subjects enrolled in this study. All data collected during the course of this study must be reviewed and verified for completeness and accuracy by the investigator. All case report forms must be completed by designated study personnel. The completed case report forms must be reviewed, signed and dated by the Investigator or designee in a timely fashion.

All data will be collected using electronic data collection, stored as indicated in [Section 14.2](#), and will be submitted according to the timelines indicated in [Table 14.3](#).

Table 14.3 Data Submission Schedule

Form	Submission Timeline
Eligibility Checklist	Complete prior to registration
On Study Forms	Within 14 calendar days of registration
Baseline Assessment Forms	Within 14 calendar days of registration
Treatment Forms	Within 10 calendar days of treatment administration
Adverse Event Report Forms	Within 7 calendar days of AE assessment/notification
Response Assessment Forms	Within 10 calendar days of the response assessment
Other Assessment Forms (concomitant medications)	Within 10 calendar days of the assessment
Off Treatment/Off Study Forms	Within 10 calendar days of end of treatment/study
Follow up/Survival Forms	Within 14 calendar days of the follow up activity

14.4 Regulatory Records

The investigator will maintain regulatory records, including updating records in accordance with Good Clinical Practice guidelines and FDA regulations.

15.0 ADHERENCE TO THE PROTOCOL

It is understood that deviations from the protocol should be avoided, except when necessary to eliminate an immediate hazard to a research participant. Protocol deviations may be on the part of the subject, the investigator, or study staff.

All deviations from the protocol must be documented in study subject source documents and promptly reported. The Study PI will report the deviation according to City of Hope's deviation policy for reporting deviations (See [Section 8.0](#)).

16.0 STUDY OVERSIGHT, QUALITY ASSURANCE, AND DATA & SAFETY MONITORING

16.1 All Investigator Responsibilities

An investigator is responsible for ensuring that an investigation is conducted according to the signed investigator statement, the investigational plan, and applicable regulations; for protecting the rights, safety, and welfare of subjects under the investigator's care; and for the control of drugs under investigation.

All investigators agree to:

- Conduct the study in accordance with the protocol and only make changes after notifying the Sponsor (or designee), except when necessary to protect the safety, rights or welfare of subjects.
- Personally conduct or supervise the study (or investigation).
- Ensure that the requirements relating to obtaining informed consent and IRB review and approval meet federal guidelines, as stated in § 21 CFR, parts 50 and 56.
- Report to the Sponsor or designee any AEs that occur in the course of the study, in accordance with §21 CFR 312.64.
- Ensure that all associates, colleagues and employees assisting in the conduct of the study are informed about their obligations in meeting the above commitments.
- Maintain adequate and accurate records in accordance with §21 CFR 312.62 and to make those records available for inspection with the Sponsor (or designee).
- Ensure that an IRB that complies with the requirements of §21 CFR part 56 will be responsible for initial and continuing review and approval of the clinical study.
- Promptly report to the IRB and the Sponsor all changes in the research activity and all unanticipated problems involving risks to subjects or others (to include amendments and IND safety reports).
- Seek IRB and Sponsor approval before any changes are made in the research study, except when necessary to eliminate hazards to the patients/subjects.
- Comply with all other requirements regarding the obligations of clinical investigators and all other pertinent requirements listed in § 21 CFR part 312.

16.2 Study Principal Investigator Responsibilities

The Study Principal Investigator is responsible for the conduct of the clinical trial, including overseeing that sponsor responsibilities as defined in § 21 CFR 312.

16.3 Protocol Management Team (PMT)

Refer to [Section 8.0](#).

16.4 Auditing

Clinical site auditing is conducted to ensure that the rights of human subjects are protected, that the study is implemented in accordance with the protocol and regulatory requirements, and that the quality and integrity of study data and data collection methods are maintained. Auditing for this study will be performed by the City of Hope Office of Clinical Trials Auditing and Monitoring (OCTAM).

Documentation of audit activities and findings by OCTAM will be provided to the study team, the PI, and the COH DSMC.

16.5 City of Hope Data and Safety Monitoring Committee

The DSMC is a multidisciplinary committee charged with overseeing the monitoring of safety of participants in clinical trials, and the conduct, progress, validity, and integrity of the data for all clinical trials that are sponsored by City of Hope. The committee is composed of clinical specialists with experience in oncology and who have no direct relationship with the study. The committee reviews the progress and safety of all active research protocols that are not monitored by another safety and data monitoring committee or board.

The COH Data and Safety Monitoring Committee (DSMC) will review and monitor toxicity and accrual data from this trial. Information that raises any questions about participant safety will be addressed with the Principal Investigator, statistician and study team. Refer to [Section 8.0](#) for details.

17.0 ETHICAL AND REGULATORY CONSIDERATIONS

17.1 Ethical Standard

This study will be conducted in conformance with the principles set forth in *The Belmont Report: Ethical Principles and Guidelines for the Protection of Human Subjects of Research* (US National Commission for the Protection of Human Subjects of Biomedical and Behavioral Research, April 18, 1979) and the Declaration of Helsinki.

17.2 Regulatory Compliance

This study is to be conducted in compliance with the IRB approved **protocol** and according to the following considerations:

- US Code of Federal Regulations (CFR) governing clinical study conduct
 - Title 21 Part 11 – Electronic Records; Electronic Signatures
 - Title 21 Part 50 – Protection of Human Subjects
 - Title 21 Part 54 – Financial Disclosure by Clinical Investigators
 - Title 21 Part 56 – Institutional Review Boards
 - Title 21 Part 58 – Good Laboratory Practice for Nonclinical Laboratory Studies
 - Title 21 Part 312 – Investigational New Drug Application
 - Title 45 Part 46 – Protection of Human Subjects
- US Federal legislation, including but not limited to
 - Health Insurance Portability and Accountability Act of 1996
 - Section 801 of the Food and Drug Administration Amendments Act
- State of California Health and Safety Code, Title 17
- Institutional policies and procedures

17.3 Institutional Review Board

In accordance with City of Hope policies, an Institutional Review Board (IRB) that complies with the federal regulations at 45 CFR 46 and 21 CFR 50, 56 and State of California Health and Safety code, Title 17, must review and approve this protocol and the informed consent form prior to initiation of the study. All institutional, NCI, Federal, and State of California regulations must be fulfilled.

Any documents that the IRB may need to fulfill its responsibilities (such as protocol, protocol amendments, Investigator's Brochure, consent forms, information concerning patient recruitment, payment or compensation procedures, or other pertinent information) will be submitted to the IRB. The IRB's written unconditional approval of the study protocol and the informed consent document will be in the possession of the investigator before the study is initiated.

The IRB will be informed of revisions to other documents originally submitted for review; serious unexpected or unanticipated adverse experiences occurring during the study, and any additional adverse experiences in accordance with the standard operating procedures and policies of the IRB; new information that may affect adversely the safety of the patients of the conduct of the study; an annual update and/or request for re-approval; and when the study has been completed.

Any amendment to the protocol document and accompanying informed consent document/template, as developed and provided by the PI, will require review and approval by the COH IRB before the changes are implemented in the study.

17.4 Informed Consent

The Principal Investigator or IRB approved named designate will explain the nature, duration, purpose of the study, potential risks, alternatives and potential benefits, and all other information contained in the informed consent document. In addition, they will review the experimental subject's bill of rights and the HIPAA research authorization form. Prospective participants will be informed that they may withdraw from the study at any time and for any reason without prejudice, including as applicable, their current or future care or employment at City of Hope or any relationship they have with City of Hope. Prospective participants will be afforded sufficient time to consider whether or not to participate in the research.

After the study has been fully explained, written informed consent will be obtained from either the prospective participant or his/her guardian or legal representative before study participation. The method of obtaining and documenting the informed consent and the contents of the consent must comply with the ICH-GCP and all applicable regulatory requirements.

Before implementing any study procedure, informed consent shall be documented by the use of a written consent form approved by the IRB and signed and dated by the prospective participant or his/her legally authorized representative at the time of consent. A copy of the signed informed consent will be given to the participant or his/her legally authorized representative. The original signed consent must be maintained by the investigator and available for inspection sponsor designated representatives, or regulatory authority at any time.

Informed consent is a process that is initiated prior to the individual agreeing to participate in the study and continues throughout study participation

17.5 Participant Withdrawal

Participants may withdraw from the study at any time and for any reason without prejudice. The withdrawal must be documented per institutional policies.

Participant withdrawal may consist of any of the following with regard to study procedures and data collection:

- Withdrawal from study treatment, but agreement to continue with active study procedures (safety visit) and chart review and survival follow-up.
- Withdrawal from study treatment and all active procedures, but agreement for chart review and survival follow-up.
- Withdrawal from study treatment, all active procedures, and any future data collection.

17.6 Special and Vulnerable Populations

17.6.1 Inclusion of Women and Minorities

Women are excluded from participation because prostate cancer is a disease of men. The study is open to any male regardless of ethnicity. If differences in outcome that correlate to racial or ethnic identity are noted, accrual may be expanded or additional studies may be performed to investigate those differences more fully.

17.6.2 Exclusion of Pediatric Patients

Pediatric recipients (children <18 years old of age) are excluded from this study because prostate cancer is not present in this population.

17.6.3 HIV Positive Individuals

Patients with controlled HIV will be included because those with well-controlled disease should not be at increased risk of developing neutropenia compared to other patients.

17.6.4 Vulnerable Populations

45 CFR §46.111 (a)(3) and 45 CFR §46, Subparts B-D identifies children, prisoners, pregnant women, mentally incapacitated persons, or economically or educationally disadvantaged persons as vulnerable populations.

Adults lacking capacity to consent are not excluded from participation. This study does not pose additional risks for adults lacking capacity than for the general population. In such instances, informed consent will be sought and documented from the prospective participant's legally authorized representative in agreement with institutional policies and local IRB approval.

17.7 Participant Confidentiality

Participant confidentiality is strictly held in trust by the investigators, study staff, and the sponsor(s) and their agents. This confidentiality is extended to cover testing of biological samples in addition to any study information relating to participants.

This research will be conducted in compliance with federal and state requirements relating to protected health information (PHI), including the requirements of the Health Insurance Portability and Accountability Act of 1996 (HIPAA). HIPAA regulations require a signed participant authorization informing the participant of the nature of the PHI to be collected, who will have access to that information and why, who will use or disclose that information, and the rights of a research participant to revoke their authorization for use of their PHI. In the event that a participant revokes authorization to collect or use PHI, the investigator, by regulation, retains the ability to use all information collected prior to the revocation of participant authorization. For participants that have revoked authorization to collect or use PHI, attempts should be made to obtain permission to collect at least vital status (i.e. that the participant is alive) at the end of their scheduled study period.

Release of research results should preserve the privacy of medical information and must be carried out in accordance with Department of Health and Human Services Standards for Privacy of Individually Identifiable Health Information, 45 CFR 164.508. When results of this study are reported in medical journals or at meetings, identification of those taking part will not be disclosed and no identifiers will be used.

Medical records of participants will be securely maintained in the strictest confidence, according to current legal requirements. Data will be entered, analyzed and stored in encrypted, password protected, secure computers that meet all HIPAA requirements. All data capture records, drug accountability records, study reports and communications will identify the patient by initials and the assigned patient number.

The investigator/institution will permit direct access to source data and documents by sponsor representatives, the FDA, and other applicable regulatory authorities. The access may consist of trial-related monitoring/auditing, IRB reviews, and FDA/regulatory authority inspections. The participant's confidentiality will be maintained and will not be made publicly available to the extent permitted by the applicable laws and regulations.

17.8 Conflict of Interest

Any investigator who has a conflict of interest with this study (patent ownership, royalties, or financial gain greater than the minimum allowable by their institution, etc.) must have the conflict reviewed by a properly constituted Conflict of Interest Committee with a Committee-sanctioned conflict management plan that has been reviewed and approved by the study Sponsor (City of Hope) prior to participation in this study. All City of Hope investigators will follow the City of Hope conflict of interest policy.

17.9 Financial Obligations, Compensation, and Reimbursement of Participants

Radium Ra 223 dichloride will be provided free of charge to participants.

Neither the research participant nor the insurance carrier will be responsible for the research procedures related to this study.

The standard of care drug(s) and standard of care procedures provided will be the responsibility of the research participant and/or the insurance carrier. The research participant will be responsible for all copayments, deductibles, and other costs of treatment and diagnostic procedures as set forth by the insurance carrier. The research participant and/or the insurance carrier will be billed for the costs of treatment and diagnostic procedures in the same way as if the research participant were not in a research study.

In the event of physical injury to a research participant, resulting from research procedures, appropriate medical treatment will be available at the City of Hope to the injured research participant, however, financial compensation will not be available.

The research participant will not be paid for taking part in this study.

17.10 Publication/Data Sharing

Neither the complete nor any part of the results of the study carried out under this protocol, nor any of the information provided by City of Hope for the purposes of performing the study, will be published or passed on to any third party without the written approval of Study PI. Any investigator involved with this study is obligated to provide City of Hope with complete test results and all data derived from the study.

The preparation and submittal for publication of manuscripts containing the study results shall be in accordance with a process determined by mutual written agreement between City of Hope and Bayer. The publication or presentation of any study results shall comply with all applicable privacy laws, including, but not limited to, the Health Insurance Portability and Accountability Act of 1996.

This study will comply with the [NIH Public Access Policy](#), which ensures that the public has access to the published results of NIH funded research. It requires scientists to submit final peer-reviewed journal manuscripts that arise from NIH funds to the digital archive [PubMed Central](#) upon acceptance for publication.

In accordance with the [U.S. Public Law 110-85](#) (Food and Drug Administration Amendments Act of 2007 or FDAAA), Title VIII, Section 801, this trial will be registered onto ClinicalTrials.gov and results will be reported on ClinicalTrials.gov within 12 months of the estimated or actual completion date of the trial, whichever date is earlier.

APPENDIX A: PERFORMANCE STATUS

ECOG Performance Scale[47]	
Grade	Descriptions
0	Normal activity. Fully active, able to carry on all pre-disease performance without restriction.
1	Symptoms, but ambulatory. Restricted in physically strenuous activity, but ambulatory and able to carry out work of a light or sedentary nature (e.g., light housework, office work).
2	In bed <50% of the time. Ambulatory and capable of all self-care, but unable to carry out any work activities. Up and about more than 50% of waking hours.
3	In bed >50% of the time. Capable of only limited self-care, confined to bed or chair more than 50% of waking hours.
4	100% bedridden. Completely disabled. Cannot carry on any self-care. Totally confined to bed or chair.
5	Dead.

APPENDIX B: STAGING CRITERIA

Stage	Sub-stage	Definition
Metastasis		Systemic spread
	M0	No distant metastasis
	M1a	Non-regional lymph node metastasis
	M1b	Bone metastasis 1) Axial skeleton only 2) Extending also to peripheral skeleton
	M1c	Metastasis at other sites

APPENDIX C: DISEASE PARAMETERS AND METHODS FOR EVALUATION

Response and progression will be evaluated in this study using modified Prostate Cancer Working Group 2 criteria [43].

Disease Parameters

- **Measurable disease:**

Measurable lesions are defined as those that can be accurately measured in at least one dimension (longest diameter to be recorded) as >10mm with conventional techniques (CT, MRI, or caliper measurement) and as >20mm by chest X-ray (if clearly defined and surrounded by aerated lung.) Lymph nodes greater than 15mm on short axis are considered measurable as well. All tumor measurements must be recorded in millimeters (or decimal fractions of centimeters).

- **Non-measurable disease:**

All other lesions (or sites of disease), including small lesions (longest diameter <20 mm by chest X-ray or <10 mm using CT, MRI or caliper measurement), are considered non-measurable disease. Organomegaly, leptomeningeal disease, ascites, pleural/pericardial effusions, lymphangitis cutis/pulmonis, inflammatory breast disease, and abdominal masses (not followed by CT or MRI) are all non-measurable.

- **Target lesions:**

All measurable lesions up to a maximum of 2 lesions per organ and 5 lesions in total, representative of all involved organs, should be identified as target lesions and recorded and measured at baseline. Lymph nodes less than 15mm in the short axis cannot be used as target lesions. Target lesions should be selected on the basis of their size (lesions with the longest diameter) and their suitability for accurate repeated measurements (either by imaging techniques or clinically). A sum of the longest diameter (LD) for all target lesions will be calculated and reported as the baseline sum LD. The baseline sum LD will be used as reference by which to characterize the objective tumor response.

- **Non-target lesions:**

All other lesions (or sites of disease) including any measurable lesions over and above the 10 target lesions should be identified as non-target lesions and should also be recorded at baseline. Measurements of these lesions are not required, but the presence or absence of each should be noted throughout follow-up.

Methods for Evaluation of Measurable Disease

All measurements should be taken and recorded in metric notation using a ruler or calipers. All baseline evaluations should be performed as closely as possible to the beginning of treatment and never more than 30 days before the beginning of the treatment.

The same method of assessment and the same technique should be used to characterize each identified and reported lesion at baseline and during follow-up. Imaging-based evaluation is preferred to evaluation by clinical examination when both methods have been used to assess the antitumor effect of a treatment

- **Clinical lesions:**

Clinical lesions will only be considered measurable when they are superficial (e.g., skin nodules and palpable lymph nodes). In the case of skin lesions, documentation by color photography, including a ruler to estimate the size of the lesion, is recommended.

- **Chest x-ray:**

Lesions on chest x-ray are acceptable as measurable lesions when they are clearly defined and surrounded by aerated lung. However, CT is preferable.

- **Conventional CT and MRI:**

These techniques should be performed with cuts of 10 mm or less in slice thickness contiguously. Spiral CT should be performed using a 5 mm contiguous reconstruction algorithm. This applies to tumors of the chest, abdomen, and pelvis. Head and neck tumors and those of extremities usually require specific protocols

- **Ultrasound (US):**

When the primary endpoint of the study is objective response evaluation, US should not be used to measure tumor lesions. It is, however, a possible alternative to clinical measurements of superficial palpable lymph nodes, subcutaneous lesions, and thyroid nodules. US might also be useful to confirm the complete disappearance of superficial lesions usually assessed by clinical examination

- **Endoscopy, Laparoscopy:**

The utilization of these techniques for objective tumor evaluation has not yet been fully and widely validated. Their uses in this specific context require sophisticated equipment and a high level of expertise that may only be available in some centers. Therefore, the utilization of such techniques for objective tumor response should be restricted to validation purposes in reference centers. However, such techniques may be useful to confirm complete pathological response when biopsies are obtained.

- **Tumor markers:**

Baseline PSA is defined as the last known PSA prior to the onset of ADT (anti-androgen or LHRH agonist/antagonist). PSA response criteria will be a part of overall response assessment and will also be recorded as a separate PSA response criteria. They are follows:

- PSA CR - PSA <0.04 confirmed at least 3 weeks later
- PSA PR - PSA decline by >50 % from baseline, confirmed at least 3 weeks later
- PSA SD - PSA not meeting criteria for CR, PR or PD

- PSA PD - PSA increase by $\geq 25\%$ over baseline and to at least PSA >2 ng/mL confirmed at least 3 weeks later

- **Cytology, Histology:**

These techniques can be used to differentiate between partial responses (PR) and complete responses (CR) in rare cases (e.g., residual lesions in tumor types, such as germ cell tumors, where known residual benign tumors can remain).

The cytological confirmation of the neoplastic origin of any effusion that appears or worsens during treatment when the measurable tumor has met criteria for response or stable disease is mandatory to differentiate between response or stable disease (an effusion may be a side effect of the treatment) and progressive disease.

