APPENDIX D: RESPONSE CRITERIA

Response and progression will be evaluated in this study using modified Prostate Cancer Working Group 2 criteria [43].

Evaluation of Target Lesions

Complete Response (CR):	Disappearance of all target lesions. Lymph node CR is when the lymph node has decreased to less than 10mm in the short axis.
Partial Response (PR):	At least a 30% decrease in the sum of the longest diameter (LD) of target lesions, taking as reference the baseline sum LD.
Progressive Disease (PD):	At least a 20% increase in the sum of the LD of target lesions, taking as reference the smallest sum LD recorded since the treatment started (including the baseline scan if that is the smallest), and at least a 5mm increase or the appearance of new lesions.
Stable Disease (SD):	Neither sufficient shrinkage to qualify for PR nor sufficient increase to qualify for PD, taking as reference the smallest sum LD since the treatment started.

Evaluation of Non-Target Lesions

Complete Response (CR)	Disappearance of all non-target lesions and PSA level <0.04 (undetectable)
Incomplete Response/Stable Disease (SD)	Persistence of one or more non-target lesion(s) and/or of PSA ≥ 0.04 but no increase $\geq 25\%$ over baseline and to at least PSA >2 ng/mL
Progressive Disease (PD):	Appearance of one or more new lesions and/or unequivocal progression of existing non-target lesions. . PSA increase by $\geq 25\%$ over baseline and to at least PSA >2 ng/mL . However, unequivocal progression should not normally trump target disease status. It must be representative of overall disease status change, not a single lesion increase

Although a clear progression of “non-target” lesions only is exceptional, the opinion of the treating physician should prevail in such circumstances.

Evaluation of Best Overall Response

The best overall response is the best response recorded from the start of the treatment until disease progression/recurrence (taking as reference for progressive disease the smallest measurements recorded since the treatment started). The patient's best response assignment will depend on the achievement of measurement criteria, but confirmation is not necessary.

Target Lesions	Non-Target Lesions	New Lesions	PSA	Overall Response
CR	CR	No	<0.04	CR
CR	Non-CR/Non-PD	No	Decline by >50% from baseline –pre ADT	PR
PR	Non-PD	No	Decline by >50% from baseline –pre ADT	PR
SD	Non-PD	No	No increase by 25 % over baseline and to a value of >2 ng/dL	SD

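### Target nodes are admitted and called CR by short axis but summed by longest diameter, so the target-lesion categories can conflict and some nodal regrowth can escape PD by the sum

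*Combined protocol and SAP*

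**What the plan says.** Three rules use a node's short axis:

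- Measurability (Appendix C, Measurable disease): "Lymph nodes greater than 15mm on short axis are considered measurable as well".
- Admission as a target (Appendix C, Target lesions): "Lymph nodes less than 15mm in the short axis cannot be used as target lesions".
- Complete response (Appendix D, Evaluation of Target Lesions): "Lymph node CR is when the lymph node has decreased to less than 10mm in the short axis".

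Three rules use longest diameter (LD) for every target, nodes included:

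- The tumour sum (Appendix C, Target lesions): "A sum of the longest diameter (LD) for all target lesions will be calculated and reported as the baseline sum LD".
- PR (Appendix D): "At least a 30% decrease in the sum of the longest diameter (LD) of target lesions, taking as reference the baseline sum LD".
- PD (Appendix D), relative part: "At least a 20% increase in the sum of the LD of target lesions, taking as reference the smallest sum LD recorded since the treatment". The absolute part of the same rule adds this condition: "and at least a 5mm increase or the appearance of new lesions".

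SD is whatever qualifies for neither PR nor PD, so it also rests on LD. Nothing in either appendix puts a node's short axis into the sum, and nothing says which call prevails if the two dimensions disagree.

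**The concern.** One lesion is judged on two axes. The axis that decides whether a node is diseased enough to be a target, and whether it has cleared, is not the axis that decides PR or PD. The categories can then disagree on a single scan, and a node can return above the size that made it a target without moving the sum enough to count.

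Radiographic progression is a component of TTF (primary) and PFS in Table 12.1, and duration of response ends at recurrent or progressive disease. Section 3.1 requires at least one bone lesion, permits a node, and accepts bone scan as documentation of metastases. A man whose bone disease cannot be measured can therefore have a node as his only target lesion. Scheduled tumour evaluation in follow-up is every 6 months, with a further one at PSA progression (Section 11.0). A regrowth that misses PD on one scheduled scan may wait about 6 months for the next.

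**Working it through.** The plan states no figure on this point, so there is none to reproduce. The thresholds come from Appendices C and D. The node sizes are illustrative assumptions, because the documents give none. Sizes are short axis x LD in mm, and the node is the sole target.

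**Rules applied.** Target: short axis at least 15. Nodal CR: short axis < 10. PR: (LD now − LD baseline) / LD baseline ≤ −30%. PD without new lesions: (LD now − LD nadir) / LD nadir ≥ 20% and LD now − LD nadir ≥ 5 mm.

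**1. CR without the PR fall.** 16x30 → 9.5x22. The short axis of 9.5 is below 10, so CR. LD: (22 − 30)/30 = −26.7%, so PR is not met and the sum reads SD. In a second example, 16x24 → 9x20, LD: (20 − 24)/24 = −16.7%. This needs the node to become more elongated. If it keeps its shape, 15 → 10 mm is −33.3% on both axes and PR is met.

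**2. CR and PD on the same scan.** Nadir 9x20 → 9.5x25. The short axis is still below 10, so CR. LD: (25 − 20)/20 = +25% and +5 mm, so PD.

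**3. Regrowth that misses PD.** Nadir 9x22 → 17x26. Short axis: (17 − 9)/9 = +88.9%, again above 15 mm. LD: (26 − 22)/22 = +18.2% and +4 mm. Both PD limits are missed.

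**4. When regrowth does not escape.** Shape kept, 9x13.5 → 18x27: +13.5 mm and +100%, so PD. Likewise 9x12 → 18x18: +6 mm and +50%, so PD. Since LD cannot be smaller than the short axis, a node doubling from 9 to 18 mm ends with LD of at least 18. To miss the 5 mm limit its nadir LD must exceed 18 − 5 = 13 mm (aspect ratio 13/9 = 1.44). To miss the 20% limit it must exceed 18/1.2 = 15 mm. Escape therefore needs a nadir LD above 13 mm and growth mainly across the short axis.

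**5. Same cases with the short axis in the sum.**

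| Case | Short axis | Change | Call |
|---|---|---|---|
| 1 | 16 → 9.5 | −40.6% | PR threshold met, consistent with CR |
| 2 | 9 → 9.5 | +0.5 mm | not PD, consistent with CR |
| 3 | 9 → 17 | +8 mm, +88.9% | PD |

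A node going from at least 15 to below 10 mm always falls by more than (15 − 10)/15 = 33.3%. If all non-nodal targets also disappear, the whole sum falls by more than one third, so target CR always implies the PR threshold. A CR/PD clash then remains possible for a sole node only when its nadir is below 10 − 5 = 5 mm. A written rule for regrowth would settle that.

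**The case against.** The strongest reply is that little follows from the mismatch, and much of that reply stands.

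- A reader might infer that any relapse doubling a node's short axis goes uncounted. The documents do not support that: step 4 shows that shape-preserving growth from 9 to 18 mm is PD. Only elongated nodes growing mainly sideways escape.
- A reader might infer that ORR is understated. It is not. The overall-response table in Appendix D reads target CR directly, so failing the 30% test does not downgrade it, and ORR counts CR and PR together.
- A reader might infer that a man with one target node has his radiographic status fixed by this rule alone. He does not. His bone disease is followed as non-target, and unequivocal non-target progression or any new lesion is PD whatever the sum shows.
- TTF also ends on its PSA rule, clinical progression or resumed ADT, and PFS on PSA progression or death. PSA progression also triggers a scan.
- The sizes are hypothetical and cases 1 and 3 lie close to the limits: 30 → 21 mm would be −30% (PR), and 22 → 27 mm would be +22.7% and +5 mm (PD). Other plausible shapes miss by more, such as 9x20 → 18x22 (+10.0%, +2 mm).

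What the reply does not remove is that the appendices can give two incompatible calls for one node on one scan with no tie-break, and can leave nodal regrowth uncounted by the sum.

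**Conclusion.** The concern holds in a limited form. The target-lesion categories are not nested, can conflict, and can miss regrowth of an elongated node. The consequence is confined to the target-lesion part of radiographic progression, and to duration of response, in men with a target node. TTF or PFS is affected only if none of the other qualifying events comes first.

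The number of men exposed is not given: it lies between 0 and all 24 evaluable patients. The size of any shift in TTF cannot be calculated from the documents. The conclusion rests on the appendix wording as it stands, on reading the PD rule as 20% and 5 mm together unless new lesions appear, and on illustrative node shapes. It is worth correcting because the rule is ambiguous and the correction is cheap, not because a material bias in the primary result has been shown.

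**What to change.** 1. In Appendix C, define the sum as longest diameter for non-nodal target lesions plus short axis for nodal target lesions.
2. In Appendix D, apply that sum to PR, SD and PD, and keep nodal CR at short axis below 10 mm.
3. State how regrowth of a node already called CR is classified (recurrence, new lesion, or PD only through the sum), and which call prevails if CR and PD are both met. Duration of response and duration of complete response depend on this.
4. Apply the same rule to all patients' scans, including those already read. Because the trial is open-label and single-arm, any re-measurement is best done by a reader unaware of PSA and clinical course, and any changed event dates should be listed.

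The cost is appendix wording, recalculated sums and possibly some re-measurement. No new imaging is needed: the short axis must already be read at baseline to admit a node and at follow-up to call nodal CR. The documents do not say whether follow-up short axes are recorded on the case report form, so that should be checked first.
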